	APPENDIX.....	44

LIST OF ABBREVIATIONS

AE	Adverse Event
CFR	Code of Federal Regulations
CIOMS	Council for International Organizations of Medical Sciences
CRF	Case Report Form
FWA	Federal-Wide Assurance
GCP	Good Clinical Practice
ICF	Informed Consent Form
ICH	International Conference on Harmonisation
IEC	Independent or Institutional Ethics Committee
IRB	Institutional Review Board
ISM	Independent Safety Monitor
JAMA	Journal of the American Medical Association
MOP	Manual of Procedures
N	Number (typically refers to subjects)
NEJM	New England Journal of Medicine
NIH	National Institutes of Health
OCRA	Office of Clinical Research Affairs, DMID, NIAID, NIH, DHHS
OHRP	Office for Human Research Protections
ORA	Office of Regulatory Affairs, DMID, NIAID, NIH, DHHS
PI	Principal Investigator
QOL	Quality of Life
SAE	Serious Adverse Event
SMC	Safety Monitoring Committee
SOP	Standard Operating Procedure
VRI	Volitional Response Index
WHO	World Health Organization

STATEMENT OF COMPLIANCE

The study will be carried out in accordance with Good Clinical Practice (GCP) as required by the following:

- U.S. Code of Federal Regulations applicable to clinical studies (45 CFR 46)
- ICH GCP E6
- Completion of Human Subjects Protection Training

PROTOCOL SUMMARY

Title: Epidural Neuromodulation for Spinal Cord Injury
Short Title: ESTAND
Objectives: Primary

1. Investigate the use of epidural stimulation to facilitate volitional movement as measured by surface EMG through the Brain Motor

Control Assessment (BMCA) Volitional Response Index Magnitude
in patients with chronic spinal cord injury and motor paraplegia

Secondary

1. Map the parameter space of epidural stimulation using accelerometers to create a Clinical Decision Support System (CDSS) for patient programming
2. Investigate the ability of SCS to enable standing
3. Assess the effect of spinal cord stimulation (SCS) on the cardiovascular system

Exploratory

1. Explore the effect of SCS on urinary control
2. Explore psychiatric and quality of life (QOL) endpoints in patients with chronic spinal cord injury undergoing SCS

Endpoints

Primary: Lower extremity brain motor control assessment volitional response index magnitude

Secondary:

sEMG power generated during standing

Classification of the parameter space

Cardiovascular system endpoints: blood pressure, cardiac function, arterial stiffness

Cerebral autoregulation and associated cognition

Exploratory:

Psychiatric metrics

Quality of Life

Safety:

Physical Examination

Blood Pressure

Adverse Event Incidence

Modified Ashworth Scale Score

Population:

Chronic motor-complete paraplegic patients

Phase:

2

Number of Sites

3

enrolling participants:

Description of Study

St. Jude Medical Tripole™ 16 Lead epidural stimulator paddle, extension wire, and Proclaim™ Elite implantable pulse generator

Agent :

[figure not shown]
Study Duration:

5 years

Participant Duration:

15 months

SCHEMATIC OF STUDY DESIGN

2 INTRODUCTION: BACKGROUND INFORMATION AND SCIENTIFIC RATIONALE

2.1 BACKGROUND INFORMATION

The goal of this proposal is to establish and investigate epidural spinal cord stimulation in paraplegic patients to facilitate volitional movement. The facilitation of volitional movement through epidural spinal cord stimulation was nearly found by accident while investigating this form of neuromodulation to facilitate standing and ambulation through central pattern generation.¹ This finding represents a paradigm shift in the understanding and future treatment of spinal cord injury and demands timely investigation and optimization for a malady with currently no therapeutic intervention and significant morbidity.

Spinal cord injury is a devastating complication of trauma, often producing paraplegia or quadriplegia. In the United States, the incidence of acute spinal cord injury is relatively stable at 54 cases per million people, which was approximately 17000 cases in 2012.² stable incidence of spinal cord injury has resulted in a prevalence of approximately 273,000 patients suffering from spinal cord injury.³

Spinal cord injury carries significant chronic medical complications as well as socioeconomic ramifications. Patients with spinal cord injury of all types have significantly reduced life-expectancy with the majority deaths caused by pneumonia and septicemia.³ The chronic complications of spinal cord injury are extensive and include all physiologic systems. In particular, patients suffer from cardiovascular complications, respiratory complications, urinary and gastrointestinal complications in addition to complex pain syndromes and morbid pressure ulcers.⁴

Caring for patients with spinal cord injury requires significant healthcare utilization.⁵ During the first year of spinal cord injury, there is significant variation of cost based on type of spinal cord injury, ranging from \$340,787 for incomplete motor function to \$1,044,197 for high cervical injuries.³ The estimated lifetime costs range from 1.1 to 4.6 million depending on the age of injury and location.³ These costs do not include lost wages or productivity. Even after the first year of spinal cord injury, patients require frequent physician contact and harbor numerous medical complications such as urinary tract infections and decubitus ulcers.⁵ Despite the significant cost and impact on society and numerous clinical trials, there have been no significant strides made in the treatment of spinal cord injury.⁶

Much of the comorbidity from spinal cord injury is secondary to immobility, and it has long been hoped that facilitating ambulation would stymie progressive comorbidity. Locomotion has long been known to be inherent within the spinal cord.⁷ Central pattern generators of the spinal cord underlie spinal cord circuitry capable of facilitated locomotion.⁸ These findings have fueled the search for a method of neuromodulation capable of

utilizing intrinsic spinal cord locomotion to facilitate ambulation. Gait training has been found to confer significant improvement in the ability of the spinal cord to facilitate walking in animal models, which has led to a modern understanding of the neuroplasticity within spinal cord circuitry.⁷

Humans with incomplete spinal cord injury have been found to benefit from similar gait training, but complete spinal cord injury remains refractory to these interventions.¹ Until recently, complete spinal cord injury was thought of as spinal cord tissue neurologically isolated the brain.⁹ Hence, there have been significant efforts to develop novel methods to bridge these gaps in order to re-establish functional connectivity or prevent secondary damage.¹⁰ Due to the nature of degeneration after spinal cord injury and the complexity of structural organization of the nervous system, bridging damaged segments of the spinal cord has been found to be a difficult problem with no current successful therapies, though many in the translational pipeline.¹⁰

Epidural stimulation has relatively recently been investigated as a possible therapeutic method of modulating spinal cord circuitry to facilitate locomotion.¹ While the focus of this approach towards improving outcomes in spinal cord injury has been to provide a platform through which to support central pattern generation and potentially provide a mechanism of sustained walking in complete spinal cord injury, during testing of subthreshold stimulation in a preliminary study of human patients, volitional movement was discovered.⁹

2.2 RATIONALE

The evidence is now mounting that for spinal cord injuries that do not involve complete transection, viable tracts may remain that are unable to overcome inherent spinal cord inhibitory networks. With targeted epidural stimulation, it is possible to facilitate volitional activation of motor units of these remaining circuits.⁹

This ground-breaking finding provides a glimmer of hope for the most common mechanism of spinal cord injury, which is a crush injury from spinal fracture after motor vehicle accident. While epidural stimulation has only been performed in a very small subset of spinal cord injury, the preliminary results are astonishing with the ability to stand in patients categorized as AIS A and AIS B, essentially complete spinal cord injury, years after their original injury.⁹

Epidural spinal cord injury has been used since 1967 in patients suffering from pain.¹¹ While multiple devices are available for implantation either as percutaneous electrodes or paddles, it is a safe and quick procedure that may have long-lasting effects on neuropathic pain and its psychological manifestations for a specific subset of patients.¹¹ As a neurosurgical procedure, it is routinely performed under MAC anesthesia, usually involving the patient during the procedure to provide tailored coverage of complex pain distributions. Epidural stimulation has been found to be a relatively safe procedure for patients with neuropathic pain.¹²

Considering the paucity of treatments available for patients suffering from spinal cord injury, our proposal aims to make steps towards creating a platform for implementation and rigorous investigation of spinal cord stimulation in Minnesota. Given the long history of safe use of spinal cord stimulation for neuropathic pain, our clinical expertise in treating patients with spinal cord injury, and experience in the implantation of spinal cord stimulators, we believe expanding on the existing population of humans implanted is essential in understanding how we can improve the lives of Minnesotans with spinal cord injury. Unfortunately, we routinely care for patients after poly-trauma who suffer spinal cord injury. On an almost weekly basis, we provide stabilization procedures for patients with complete spinal cord injury at cervical and thoracic levels. We are frequently reminded of the lack of treatments available for our patients suffering from spinal cord injury. Through a partnership between Hennepin County Medical Center and the University of Minnesota, linked through a long-standing relationship as the two

main training sites for Neurosurgery residents, our proposal draws on considerable experience with clinical, basic science, and translational research.

2.3 POTENTIAL RISKS AND BENEFITS

2.3.1 KNOWN POTENTIAL RISKS

The primary risks of this intervention are related to the implantation of an epidural spinal cord stimulator. While in use for many decades for the treatment of chronic pain, it is being used in this study for chronic spinal cord injury.

Surgical risks for implantation of an epidural spinal cord stimulator include bleeding, infection, spinal cord damage (though presumed nonfunctional in this population, cerebrospinal fluid leak, need for further surgery, need for blood transfusion, and rarely death. Subjects will undergo anesthesia for implantation which also harbors risk including heart arrhythmia, pneumonia as well as rare risks such as heart attack, stroke, and death.

Device Associated Adverse Effects

Surgical risks for implantation of an epidural spinal cord stimulator include bleeding, infection, spinal cord damage (though presumed nonfunctional in this population, cerebrospinal fluid leak, need for further surgery, need for blood transfusion, and rarely death. Subjects will undergo anesthesia for implantation which also harbors risk including heart arrhythmia, pneumonia as well as rare risks such as heart attack, stroke, and death.

In addition to those risks commonly associated with surgery, the following risks are associated with implanting or using this neurostimulation system, in order of likelihood and impact:

Likely (more than 10 out of 100 people)

- Lead migration, causing changes in stimulation or reduced pain relief. Retrospective study incidence is 14%. Prospective studies report rates between 10-59%.¹³⁻¹⁵
- Lead breakage. Retrospective study incidence is 17%. The incidence for one prospective study is 4%.¹⁵

Less Likely (1 to 10 out of 100 people)

- Infection. Retrospective study incidence is 3%. Prospective study incidence is 3-4%.^{14,15}
- Hardware malfunction. Retrospective study incidence is 3%. Prospective study incidence is 2-6%.^{13,15}
- Over or understimulation: 2.6% incidence.
- Battery failure: 1.9% incidence.
- Persistent pain at the electrode or IPG site: 1.1% incidence. In one prospective study, 8% of subjects reported discomfort.¹⁴
- Loose connection: 1% incidence.

Rare (less than 1 out of 100 people) or low impact

- Unpleasant sensations or motor disturbances, including involuntary movement, caused by stimulation at high outputs
- Stimulation in unwanted places (such as radicular stimulation of the chest wall)
- Epidural hemorrhage, hematoma, spinal cord compression, or paralysis from placement of a lead in the epidural space
- Cerebrospinal fluid (CSF) leakage

- Paralysis, weakness, clumsiness, numbness, or pain below the level of the implant
- Seroma (mass or swelling) at the IPG site
- Allergic or rejection response to implant materials
- Implant migration or skin erosion around the implant

Potential Adverse Effects from Testing

- Skin abrasions
- Muscle damage from transfers
- Injury from Fall
- Hypotension
- Stroke

Participating in this trial is a significant commitment without guarantee of any benefit. Undergoing surgery, rehabilitation, and testing is a significant physical risk. Daily training and monthly appointments garner potential associated economic, social, and psychological risks including required travel for appointments and medical care, dissatisfaction with medical benefit, and prolonged postoperative recovery.

The risks associated with this study are warranted in humans because of the potential direct benefit of the study participants and the spinal cord injury community. There are no known alternative epidural spinal stimulation therapies to offer instead of surgical implantation.

Autonomic Testing

Many SCI subjects will likely sustain skin irritation from the recording electrodes. These conditions are considered to be minimal risks and are reversible.

There is some chance that subjects may sustain lowering or elevation of blood pressure, dizziness or skin abrasion from hand placements of the trainers. If these events occur, the experiment would cease immediately and the principal and co-principal investigators will be alerted if the condition persists. These conditions are considered to be minimal risks and are reversible.

It is highly unlikely that a subject would feel chest pain or high blood pressure would occur that did not resolve within several minutes. These events have not occurred in our past experience. However, if this did occur the individual would be immediately transported to the respective hospital's Emergency Unit and the principal and co-principal investigator will be notified. It is also highly unlikely that a subject would suffer a muscle strain, joint sprain or fracture from standing. These conditions are considered to be moderate risks but rarely occur. However if these events should occur, the subject would immediately stop standing training and would be evaluated the principal or co-principal investigators or the physician investigator administering the procedure. Standard medical procedures will be provided. The subject's primary physician would be notified as needed. These conditions are considered to be moderate risks and are reversible.

Orthostatic Stress Test: While undergoing this test, participants may experience dizziness, changes in blood pressure and heart rate or shortness of breath. Each participant will be closely monitored for any drastic changes in the recordings of their blood pressure, heart rate or breathing or show visible flushing of their cheeks or face.

There are no identifiable psychological, sociological, economical or legal risks to the participants.

2.3.2 KNOWN POTENTIAL BENEFITS

Preliminary studies have demonstrated regaining ability of volitional movement in some muscle groups in these paralyzed patients. In addition, improvements in urinary function and cardiovascular stability has been observed in preliminary reports. A potential benefit of this study includes regaining volitional movement while stimulation is occurring. It is unknown whether autonomic benefits will occur from stimulation. There is no payment for participating during any aspect of the study.

3 OBJECTIVES AND PURPOSE

Epidural spinal cord stimulation for the purpose of facilitating volitional movement is a new and novel neuromodulatory treatment. Epidural SCS has a long history of use for chronic pain with established medical device platforms. The purpose of this study is to investigate and establish the use of SCS for volitional movement. Specifically, establishing the disinhibitory effect of SCS in a greater population with inherent greater variability.

In addition to establishing the disinhibitory effect of SCS for cSCI, our study attempts to explore the parameter space of the spinal cord stimulator platforms in order to optimize stimulation settings for patients through the creation of a clinical decision support system (CDSS). Preliminary evidence suggests benefit to autonomic function, and this study also begins to explore the effects of SCS on cardiovascular function, urinary function, psychiatric outcomes, and quality of life, which all offer significant potential for patients suffering from chronic spinal cord injury.

In summary:

Primary

1. Investigate the use of epidural stimulation to facilitate volitional movement as measured by surface EMG through the Brain Motor Control Assessment (BMCA) Volitional Response Index Magnitude in patients with chronic spinal cord injury and motor paraplegia

Secondary

1. Map the parameter space of epidural stimulation using accelerometers to create a Clinical Decision Support System (CDSS) for patient programming
2. Investigate the ability of SCS to enable standing
3. Assess the effect of spinal cord stimulation (SCS) on the cardiovascular system

Exploratory

1. Explore the effect of SCS on urinary control
2. Explore psychiatric and quality of life (QOL) endpoints in patients with chronic spinal cord injury undergoing SCS

4 STUDY DESIGN AND ENDPOINTS

4.1 DESCRIPTION OF THE STUDY DESIGN

This is a quasi-experimental study of chronic spinal cord injury patients using same-subject preoperative and sham controls to determine primary and secondary outcomes. Testing of sham vs. stimulation phases during visits will be randomized and double blinded.

4.2.1 PRIMARY ENDPOINT

The primary endpoint is the BMCA VRI magnitude.

4.2.2 SECONDARY ENDPOINTS

Secondary endpoints include:

1. sEMG power generated during standing
2. Classification of the parameter space
3. Cardiovascular system endpoints: blood pressure, cardiac function, arterial stiffness
4. Cerebral autoregulation and associated cognition

4.2.3 EXPLORATORY ENDPOINTS

Exploratory endpoints include:

1. Psychiatric metrics
2. Quality of Life

5 STUDY ENROLLMENT AND WITHDRAWAL

5.1 PARTICIPANT INCLUSION CRITERIA

In order to be eligible to participate in this study, an individual must meet all of the following criteria:

1. 22 years of age or older
2. Able to undergo the informed consent/assent process
3. Stable, motor-complete paraplegia
4. Discrete spinal cord injury between C6 and T10
5. ASIA A or B Spinal Cord Injury Classification
6. Medically stable in the judgement of the principal investigator
7. Intact segmental reflexes below the lesion of injury
8. Greater than 1 year since initial injury and at least 6 months from any required spinal instrumentation
9. Willing to attend all scheduled appointments

5.2 PARTICIPANT EXCLUSION CRITERIA

1. Diseases and conditions that would increase the morbidity and mortality of spinal cord injury surgery (e.g. cardiopulmonary issues)
2. Inability to withhold antiplatelet/anticoagulation agents perioperatively
3. Significant dysautonomia that would prohibit rehabilitation or assisted standing or any history of CVA or MI associated with autonomic dysreflexia.. A single tilt table test with syncope, presyncope, or SBP < 50 or >200.
4. Other conditions that would make the subject unable to participate in testing/rehabilitation in the judgement of the principal investigator
5. Current and anticipated need for opioid pain medications or pain that would prevent full participation in the rehabilitation program in the judgement of the principal investigator
6. Clinically significant mental illness in the judgement of the principal investigator
7. Botulinum toxin injections in the previous 6 months
8. Volitional movements present during EMG testing in bilateral lower extremities
9. Unhealed spinal fracture
10. Presence of significant contracture

11. Presence of pressure ulcers
12. Recurrent urinary tract infection refractory to antibiotics
13. Current Pregnancy

5.3 STRATEGIES FOR RECRUITMENT AND RETENTION

Subjects will be recruited via flyer made available at each site through the neurosurgery and PM&R clinics. We anticipate limited enrollment during the first year to establish and test trial infrastructure. Expansion through the additional sites and capacity should double each year until target enrollment. After securing the initial funding source, our clinic receives weekly inquiries about the status of the proposed trial, highlighting the existing potential recruitment network. We anticipate flyers to be widely disseminated throughout this network.

Patients with chronic SCI are highly motivated and very involved in their care. Subjects will be in continuous contact with the study as they complete their home rehabilitation regimen and will be seen on a monthly basis for testing.

Subjects will receive appointment reminders the week prior to their appointments and regular phone calls if their home rehabilitation progress becomes delayed by more than one week.

Subject recruitment will be divided into two phases. In phase 1, 10 subjects will be recruited per protocol. After the recruitment of the 10th subject, recruitment will be temporarily halted. After the 6 month timepoint data collection for these 10 subjects, the safety endpoints and adverse event reports will be submitted to the FDA in a summary format. Recruitment will not continue until FDA review and approval, though additional subjects may be screened and potentially scheduled.

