10.4 DESCRIPTION OF STATISTICAL METHODS

10.4.1 GENERAL APPROACH

This study represents a single-arm quasi-experimental, multiple, sham-controlled crossover study. This design is possible because of the rapid onset and offset of the effect of epidural stimulation as previously reported. This protocol provides the opportunity to test outcome measures intensely in each individual subject over different stimulation settings with sham control longitudinally. The intention of the longitudinal assessments is to search for improvements over time with increased understanding of the stimulation parameter space. As such most outcomes utilize the repeated measures ANOVA.

Baseline data relevant to spinal cord injury movement and its adverse effects will be measured in the hopes of providing guidance for future generalizability. Descriptive statistics will be reported as means with standard deviations. Tests will be considered statistically significant when alpha is less than 0.05 for two-tailed tests. All assumptions for statistical tests will be evaluated before use of the test and corrected if necessary and possible.

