The repeated measures ANOVA will be used to compare sham and treatment where alpha is assumed to be 0.025 (two tailed) and power 0.95. The correlation between repeated measures is assumed to be 0.5. The ANOVA residuals will be assessed for normality and the groups will be assessed for homoscedasticity. If there are significant violations of these assumptions then Friedman's test will be used instead. The data will be displayed with means and 95% confidence intervals between treatment and sham for each subject and as a group over time.

Missing data will be analyzed to examine for randomness of omission. If the missing data is determined to be reasonably random, then predictive mean matching will be used for imputation. The distribution of the complete data set will be examined with and without the imputed data.

Data from subjects with incomplete data from dropout will be included in the final analysis unless the subject requested removal of their data. Incomplete data will be pooled per session.

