10.4.7.2 EFFICACY REVIEW

In this open-label study, interim analysis will be completed after every cohort of six subjects to examine primary and secondary outcomes. These preliminary analyses will have no effect on subject enrollment or early termination of the study due to efficacy.

Formal interim analysis will occur after completion of final outcome of 30 and 60 subjects to assess for efficacy.

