10.5 SAMPLE SIZE

Subjects will undergo blinded treatment and sham BMAC testing at each monthly appointment during the course of the trial. Assuming nonattendance to be approximately 25%, we expect subjects to complete at least 9 sessions. With a power of 0.95 and alpha of 0.025 for a two level ANOVA, we assume a correlation among repeat measure of 0.5. By assuming a baseline mean magnitude of 0.3 and a clinically significant change of 0.2 while assuming a within group standard deviation of 0.25 (resulting in an effect size of 0.4), we estimate that we will need at least 56 subjects to demonstrate significance for the primary outcome.

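### The plan sizes the trial at a minimum of 56 but sets a formal interim efficacy analysis at 60 completers, and states no planned enrolment, final-analysis number or boundary for the formal looks

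*Combined protocol and SAP*

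**What the plan says.** Three sections bear on how large the trial is and when it is finally analysed.

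- **5.3 (recruitment):** "Expansion through the additional sites and capacity should double each year until target enrollment". The first recruitment phase is 10 subjects, followed by a pause for FDA review. The second phase has no stated size.
- **10.5 (sample size):** "we estimate that we will need at least 56 subjects to demonstrate significance for the primary outcome". The allowance of about 25% in that section is for missed sessions, not for subjects lost.
- **10.4.7.2 (efficacy review):** "Formal interim analysis will occur after completion of final outcome of 30 and 60 subjects to assess for efficacy". Separately, "interim analysis will be completed after every cohort of six subjects to examine primary and secondary outcomes". The plan says these six-subject reviews will not affect enrolment or lead to early stopping for efficacy. That assurance is written for the six-subject reviews, not for the two formal analyses.

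On the significance level, 10.4.2 states for the primary endpoint that "alpha is assumed to be 0.025 (two tailed) and power 0.95", while the general approach in 10.4.1 says "Tests will be considered statistically significant when alpha is less than 0.05 for two-tailed tests".

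The protocol summary lists population, sites and duration without a number of subjects. Some front pages, including those at the study-schematic heading, were not available. The absence of a planned enrolment is therefore asserted only for the remaining text.

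**The concern.** An interim analysis comes before a final one. Here the second formal interim falls four subjects after the only sample size in the plan, and nothing says what follows it. A reader cannot tell whether the 60-completer analysis is an interim, the final analysis, or one that will never take place.

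Two things are at stake. First, the final test of the primary hypothesis is not tied to a number fixed in advance. The blind is broken at interim analyses (10.6.3) and demonstrated efficacy is a listed reason to stop (5.5), so that number should be fixed before any outcome is seen. Second, the formal looks have the declared purpose of assessing efficacy but carry no boundary or alpha allocation. If each is a test at the nominal level, the 0.025 is exceeded.

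**Working it through.** **Step 1: reproduce 56.** Inputs from 10.5: change 0.2, standard deviation 0.25, correlation 0.5, alpha 0.025, power 0.95, 9 sessions. The standardised difference is 0.2/0.25 = 0.8, and half of that is the plan's effect size, f = 0.4. The two-group repeated-measures formula is

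λ = f² × N × m / (1 + (m − 1)ρ), with F on 1 and N − 2 degrees of freedom.

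With m = 9 and ρ = 0.5, λ = 0.16 × N × 9/5 = 0.288N.

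| N | λ | Power |
|---|---|---|
| 30 | 8.64 | 0.714 |
| 55 | 15.84 | 0.9498 |
| 56 | 16.13 | 0.954 |
| 60 | 17.28 | 0.966 |

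So 56 is the smallest total reaching 0.95, and 60 is not what 10.5 computed. The gap is 4 subjects, or 4/56 = 7%, too large to be rounding. (This is a between-group formula although every subject receives both stimulation and sham. That is a separate question; here it only identifies where 56 comes from.)

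**Step 2: set the two sections against each other.**

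| Reading | Consequence |
|---|---|
| 56 is the analysed total | The 60-completer interim cannot occur (4 short) |
| 60 is the final analysis | 10.4.7.2 labels a final analysis as interim |
| More than 60 completers are planned | Both sections hold, but the size is stated nowhere |

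**Step 3: error rate of the formal looks.** Assume that each formal look and the final analysis test the primary hypothesis two-sided at 0.025 with no adjustment (critical value 2.241), that rejection at any of them counts as success, and that the statistics at a and b completers (a < b) are jointly normal with correlation √(a/b). For 30 and 56 that correlation is √(30/56) = 0.73; for 30 and 60 it is √(30/60) = 0.71. The overall error is the probability that at least one statistic exceeds 2.241 in absolute value under the null.

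| Analyses at | Overall type I error |
|---|---|
| 30, 56 | 4.2% |
| 30, 60 | 4.3% |
| 30, 60, 75 (assumed final) | 5.3% |
| 30, 60, 80 (assumed final) | 5.4% to 5.5% |
| 30, 60, 90 (assumed final) | 5.6% |

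Finals of 75 to 90 are assumptions; the documents give none. If the general 0.05 of 10.4.1 were applied at each look instead, the same schedules give about 8.2%, 8.3% and 10.1% to 10.7%.

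**Step 4: enrolment needed.** The documents give no subject dropout rate, so a range is assumed. Enrolment is completers divided by (1 − dropout), rounded up.

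| Assumed dropout | For 56 completers | For 60 completers |
|---|---|---|
| 0% | 56 | 60 |
| 10% | 63 | 67 |
| 20% | 70 | 75 |
| 25% | 75 | 80 |

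**The case against.** The strongest reply is that 56 is worded as a minimum. A trial with more than 60 completers satisfies both 10.5 and 10.4.7.2, and its power would be higher than stated. That stands. A reader might infer that 56 and 60 contradict each other outright, or that the 0.95 power is wrong at 60; the documents support neither. Power of 0.966 at 60 is no defect, and a floor does not fix a ceiling. What the reply does not supply is the larger planned size that would make 60 an interim.

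A reader might also infer that the team may test at 56, go on to 60 and claim whichever is significant, for an error rate of about 3.2%. The plan never names 56 as an analysis point, and that figure leaves out the 30-subject look, which is planned. Nor do the documents support reading the six-subject reviews as a way of choosing the sample size: 10.4.7.2 expressly rules out an effect on enrolment. An unnumbered target makes that harder to verify, but does not permit it.

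The error rates in Step 3 also depend on the formal looks being tests. If they are descriptive, no alpha is spent. That is a fair point, but the stated purpose is to assess efficacy, and the plan does not say they are descriptive.

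Finally, a planned number may have stood on the pages not available. It would still have to be reconciled with 10.4.7.2 and 10.5.

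**Conclusion.** The concern holds as a gap in the plan, not as an arithmetical contradiction. In the available text, a formal look labelled interim falls after the only stated size, with no planned enrolment, no final-analysis number and no boundary for the formal looks. Followed as written, the schedule gives an interim that is never reached, a final analysis under the wrong name, or a trial larger than any size stated.

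If the formal looks are unadjusted tests at two-sided 0.025, the overall type I error is about 4.2% to 4.3% with one look at 30 and a final at 56 or 60. It is 5.3% to 5.6% with looks at 30 and 60 and a final of 75 to 90. The first range is about 1.7 times the intended 2.5%; the second is a little over twice. These figures rest on the joint-normal approximation, on success being claimed at any look and, for the second range, on an assumed final size. The plan should be corrected before outcome data are reviewed.

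**What to change.** 1. In 10.5 and 10.4.7.2, state one number of analysable subjects at which the single final analysis takes place, and say which analysis set it counts. Let 5.3 refer to that number and give the planned enrolment that goes with it.
2. Relabel the 60-completer look as the final analysis, delete it, or place it below the final number.
3. If more than 60 analysable subjects are already intended, restate 10.5 with that size and its power.
4. For any formal look that remains, state either that it does not test for efficacy or that it spends a named part of the 0.025. For example, 0.001 at the look leaves at least 0.025 − 0.001 = 0.024 for the final test.

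The cost is wording in three sections, plus slightly less alpha at the final test if an interim test is kept. It should not be described as free of extra patients. Enrolment needed to reach the analysable number depends on a subject dropout rate that the documents do not give, and on the assumed range above it runs from 56 to 75 for 56 analysable subjects and from 60 to 80 for 60.
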